#### Power calculations:

Primary endpoint: A power calculation for our primary endpoint is not applicable in this pilot safety and tolerability trial.

Sample secondary (daily diuretic dose) endpoint power calculation: Based on prior literature, an estimated mean daily diuretic dose of 0.6 mg/kg with an effect size of 0.5 mg/kg, and a sample size of 15 total accrued subjects, will have 75% power to detect a difference in mean daily diuretic dose before and after study drug treatment using a two-sample t-test at the 5% level of significance.

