#### Aims

The specific aims of this investigation include:

- 1. To evaluate the safety and tolerability of SGLT2i therapy in patients with ATTR-CM and DM or CKD on oral loop diuretic therapy
- 2. To evaluate the change in oral loop diuretic daily dose in patients with ATTR-CM and DM or CKD on an SGLT2i.

- 3. To evaluate the effect of SGLT2i therapy on body composition in patients with ATTR-CM and DM or CKD.
- 4. To evaluate the effect of SGLT2i therapy on echocardiographic features of volume status in patients with ATTR-CM and DM or CKD.

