#### **Statistical Procedures:**

The primary endpoint for this pilot trial will be a serious adverse event rate greater than 30%, which is an acceptable rate, based on prior clinical trial data with sodium-glucose cotransporter 2 inhibitors in subjects with heart failure over a 3 month period. Secondary endpoints will include mean change in daily diuretic dose (mg/kg of furosemide equivalence), mean change in body weight (kg) and total water content (kg), and mean change in Kansas City Cardiomyopathy Questionnaire (KCCQ) score and Short Physical Performance Battery (SPPB) score. In preliminary analyses, we will describe the baseline characteristics of subjects. In particular, we will present summary measures on patient age, sex, diabetes status, renal function, NT-proBNP level, KCCQ score, SPPB score, daily diuretic dose, echocardiographic features, and body composition analysis (including body weight and total water content). Continuous variable distributions will be assessed for normality and skewness, and log transform applied when appropriate. A matched-paired t-test will be used to test for a significant difference in the means of measured secondary endpoints pre- and post-treatment with empagliflozin 10 mg oral daily for 3 months.

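### The plan's only power figure (75%, daily diuretic dose) assumes a change equal to 83% of the mean, states no SD, and uses a two-sample test where a paired one is planned

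*Combined protocol and SAP*

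**What the plan says.** Change in oral loop diuretic dose is the second aim: "To evaluate the change in oral loop diuretic daily dose in patients with ATTR-CM and DM or CKD on an SGLT2i". Statistical Procedures lists mean change in daily dose, in mg/kg of furosemide equivalents, among the secondary endpoints and fixes the test: "A matched-paired t-test will be used to test for a significant difference in the means of measured secondary endpoints", comparing values before and after three months of treatment.

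Power calculations states that no power calculation applies to the primary safety endpoint. It then gives a sample calculation for diuretic dose, which is the only power figure in the plan. Its inputs, attributed to prior literature, are "an estimated mean daily diuretic dose of 0.6 mg/kg with an effect size of 0.5 mg/kg". The number of subjects is 15 in total, and the test named is a two-sample t-test at 5%. The stated result is that such a trial "will have 75% power to detect a difference in mean daily diuretic dose before and after study drug treatment".

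The section gives no SD of the dose or of the change, no correlation between the two measurements, no direction of effect, no sidedness and no allowance for dropout. The synopsis describes the design as single-arm.

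**The concern.** Three features of the sentence stop it from describing the planned analysis.

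- **Effect.** A difference of 0.5 on a mean of 0.6 is very large, and the text does not explain it beyond the reference to prior literature. A fall of that size would leave a mean of 0.1 mg/kg; a rise would nearly double the dose.
- **SD.** Power for a difference in mg/kg cannot be calculated without an SD, and none is given.
- **Test.** A two-sample test compares independent groups. Here the same subjects are measured twice, and the analysis is paired.

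What is at stake is how a non-significant diuretic result will be read. The synopsis lists diuretic dose first among the secondary outcomes, and the section on future use of data and specimens says that the data may inform larger trials. A reader who takes 75% power at face value, without noticing the size of effect behind it, could treat a null result as evidence that the drug does not spare diuretics.

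**Working it through.** **Inputs from the plan.** Mean dose 0.6 mg/kg; difference 0.5 mg/kg; n = 15; alpha 5%; power 75% (Power calculations). Paired t-test (Statistical Procedures). **Assumptions made here:** two-sided testing, all 15 subjects analysed, and every SD below.

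**1. Size of the assumed effect.** 0.5 / 0.6 = 0.833, or 83% of the mean. Changes of 25% and 50% of the mean are 0.25 × 0.6 = 0.15 and 0.50 × 0.6 = 0.30 mg/kg.

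**2. Trying to reproduce the 75%.** Power comes from the noncentral t distribution:

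- two groups of n each: noncentrality = (difference / SD) × √(n/2), with 2n − 2 degrees of freedom;
- n pairs: noncentrality = (mean change / SD of change) × √n, with n − 1 degrees of freedom.

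Without an SD, neither can be evaluated from the plan's inputs. Candidate readings give:

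| Reading | Power |
|---|---|
| Two groups of 15, difference 0.5, SD 0.5 (ratio 1.0) | 75.3% |
| 15 pairs, 0.5 taken as a standardised effect | 43.8% |
| Two groups of 15, 0.5 taken as a standardised effect | 26.2% |

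The first reading matches, but its SD is not in the document and it needs 30 independent observations in two groups. Supposing that 0.5 is a standardised effect given a unit by mistake does not recover the figure.

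**3. What 15 pairs can detect.** Solving the paired formula for 75% power gives mean change / SD of change = 0.731. For this to correspond to 0.5 mg/kg, the SD of change must be 0.5 / 0.731 = 0.684 mg/kg.

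**4. Is 0.684 a reasonable SD of change?** With the same SD at both visits, SD of change = SD × √(2(1 − ρ)), where ρ is the correlation between the two measurements. With SD 0.5 per visit, 0.684² = 0.468 = 2 × 0.25 × (1 − ρ), so ρ = 1 − 0.468/0.5 = 0.06. That is almost no correlation between two doses in the same person, so 0.684 is a pessimistic value.

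**5. Paired power for smaller changes, n = 15.**

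| SD of change (mg/kg) | ρ if SD per visit is 0.5 | 0.15 mg/kg (25%) | 0.30 mg/kg (50%) |
|---|---|---|---|
| 0.684 | 0.06 | 12% | 35% |
| 0.50 | 0.50 | 19% | 58% |
| 0.25 | 0.875 | 58% | 99% |

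**6. SD needed for 75% power.** For a 50% change, 0.30 / 0.731 = 0.41 mg/kg or less. For a 25% change, 0.15 / 0.731 = 0.205 mg/kg or less.

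**The case against.** The strongest reply is that the trial may have good power after all. The planned test is paired, subjects must be on stable oral diuretics at entry, and two doses in one person are likely to be correlated. With SD 0.5 per visit and ρ = 0.7, the SD of change is 0.5 × √0.6 = 0.387, and power for a 50% change is 80%. This stands. A reader might infer that the trial is badly underpowered for any ordinary dose change, or that it could detect only near-complete diuretic withdrawal. The documents support neither: the SD is missing, and plausible values of it lead to very different answers.

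A reader might also argue that a subject starting below 0.5 mg/kg cannot fall by 0.5, so the assumed effect is impossible for many. That confuses individuals with the endpoint, which is a mean change; the mean can fall by 0.5 without every subject doing so.

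Nor should the 75% be taken as the justification for 15 subjects. The plan labels it a sample calculation for a secondary endpoint, and presents 15 as the accrual target of a pilot whose primary outcome is safety and tolerability. It does not say that 15 was derived from the diuretic endpoint.

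Finally, the inputs are attributed to literature that is not reproduced, so 0.5 mg/kg cannot be called wrong, and the text speaks only of a difference, not a fall. This also stands. It does not cure the missing SD or the mismatch between tests, and it leaves an effect of 83% of the mean unexplained.

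**Conclusion.** The concern holds in a limited form. The 75% does not describe the planned analysis: it rests on a difference of 83% of the stated mean, gives no SD, and uses a test for independent groups in a single-arm trial to be analysed with a paired t-test. It cannot be reproduced from the stated inputs; the match found (75.3%) requires two groups of 15 and an SD of 0.5 mg/kg that the plan does not state.

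Power for smaller changes is undetermined rather than shown to be low. Over SDs of change from 0.684 down to 0.25 mg/kg, it runs from about 12% to 58% for a 25% change and from 35% to 99% for a 50% change. These ranges assume two-sided testing and 15 complete pairs; dropout would lower them.

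The matter affects how a secondary endpoint of a pilot is interpreted. It does not affect the primary safety aim.

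**What to change.** Replace the diuretic sentence in Power calculations with a paired calculation that:

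- states that 15 pairs give 75% power, two-sided at 5%, for a mean change of 0.73 SD of the change;
- gives the SD of the within-patient change in mg/kg with its source or, if no source exists, a range;
- tabulates power for 25% and 50% changes (0.15 and 0.30 mg/kg) over that range;
- either justifies 0.5 mg/kg from the cited literature or drops it.

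In Statistical Procedures, say that the diuretic endpoint will be reported as a mean change with a 95% confidence interval, and that a non-significant result will not be read as absence of diuretic sparing. The expected precision can be stated in advance. The half-width is about 2.145 × SD of change / √15, which is 0.38, 0.28 and 0.14 mg/kg for SDs of 0.684, 0.50 and 0.25.

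The cost is protocol wording. The stated power may become less favourable; no more patients, visits or measurements are needed.
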